5. SAMPLE SIZE DETERMINATION

Formal sample size calculations were not performed. The number of subjects was chosen based on feasibility and was considered sufficient to meet the study objectives.

6. PROGRAMMING SPECIFICATIONS

The programming specifications, including the mock-up validity listings, analysis tables, figures, and data listings, as well as the derived database specifications, will be prepared in stand-alone documents. The programming specification documents will be finalized prior to database lock.

7. INTERIM ANALYSIS

No interim analysis is planned.

8. APPENDICES

Appendix A: Study Assessments and Timing Window

Table 2. Study Assessments for Cohort 1

Visit number	Screening	Treatment Period															Follow-Up	
	1	2	3	4	5	6	7	8	9	10	11	12	13	14	15	16	17	18
Time point (study day)	-14 to -1	0	1 (±1 h)	2 (±2 h)	5 ^P (±4 h)	7 (±6 h)	12 ^P (±6 h)	14 (±6 h)	19 ^P (±6 h)	21 (±6 h)	28 (±6 h)	29 (±1 h)	30 (±2 h)	33 (±4 h)	42 (±3 d)	56 (±5 d)	84 (±5 d)	112 or ET (±5 d)
Informed consent	X																	
Demographics/medical history	X																	
Inclusion/exclusion	X																	
Physical examination ^a	X	X				X		X		X	X				X	X	X	X
Vital signs ^b	X	X	X	X	X	X	X	X	X	X	X	X	X	X	X	X	X	X
Pulse oximetry ^c		X				X		X		X	X							
Clinical safety labs ^d	X	X				X		X		X	X			X	X	X	X	X
Pregnancy test ^e	X	X														X		X
Hepatitis and HIV screen	X																	
12-lead ECG ^f	X	X					X				X					X		
Tetanus and VZV antibodies ^g		X														X	X	X
PDAI		X				X		X		X	X			X	X	X	X	X
PK sampling ^h		X	X	X	X						X	X	X	X				
Immunogenicity ⁱ		X						X			X					X	X	X
Study drug administration ^j		X				X		X		X	X							
Immunoglobulins (IgG, IgA, IgM) and IgG subtypes (IgG1-4) ^k	X	X	X	X	X	X	X	X	X	X	X	X	X	X	X	X	X	X ^q
CIC		X			X	X	X	X	X	X	X			X	X	X	X	X
Anti-Dsg (1 and 3) antibody titers	X	X				X		X						X		X	X	X
C3 and AECA ^l		X						X						X		X	X	X
FCGR2A by buccal swab ^m		X																
RNAseq		X						X						X		X	X	X
Urine IgG		X						X						X		X	X	X
Immunophenotyping ⁿ		X									X					X		
Exploratory pemphigus immune response biomarkers		X			X	X	X	X	X	X	X			X	X	X	X	X

Optional skin biopsy		X	X	X				X					X		X	X	
Photography ^o		X											X		X	X	X
Adverse events	To be collected from the date that the ICF is signed through the last study visit																
Concomitant medications	To be collected from within 14 days prior to Day 0 through the last study visit																

Abbreviations: CIC = circulating immune complexes; d = days; ECG = electrocardiogram; ET = early termination; h = hour(s); HIV = human immunodeficiency virus;
ICF = informed consent form; PDAI = Pemphigus Disease Area Index; PK = pharmacokinetic; VZV = varicella zoster virus.

- a. Complete physical examination, including weight, to be performed. Height and BMI will be additional assessments conducted at screening.
- b. Vital sign measurements (sitting blood pressure, heart rate, respiratory rate, and oral temperature) to be obtained after 5 minutes of seated rest. Any abnormal measurements are to be repeated after 5 minutes of rest. On Days 0, 7, 14, 21, and 28, vital sign measurements will be collected immediately prior to the infusion; 15, 30, and 45 minutes after the start of the infusion; at completion of the infusion; and 30 minutes, 1 hour, and 2 hours following completion of the infusion.
- c. Pulse oximetry: On Days 0, 7, 14, 21, and 28, pulse oximetry to be measured immediately prior to the infusion; 15, 30, and 45 minutes after the start of the infusion; at completion of the infusion; and 30 minutes, 1 hour and 2 hours following completion of the infusion.
- d. Clinical safety labs: hematology, clinical chemistry, and urinalysis (See Protocol Section 7.5 for a complete list). Full clinical safety laboratory draws will be collected at screening and on Days 0, 7, 14, 21, 28, 33, 42, 56, 84, and 112.
- e. Pregnancy test (women of childbearing potential only): To be performed at time of screening, prior to first dose of SYNT001 on Day 0, and on Days 56 and 112. Urine or serum test is acceptable; however, positive urine tests must be confirmed with serum testing.
- f. Digital 12-lead ECG to be obtained in triplicate at least 1 to 2 minutes apart and after 5 minutes of rest in a supine position. See Protocol Section 7.6 for additional information. On Days 0 and 28 to be obtained 5 minutes after the completion of infusion. Day 12 ECG will be collected only if the visit is conducted at the study site.
- g. Serology: Testing at Day 56 will not be done for any subject whose baseline titer is below the level of detection. If the Day 56 results are greater than 30% below the baseline value, or if the subject falls below the level of detection, the subject will be re-tested at Day 84; if still below the baseline value (or level of detection), the subject will be re-tested at Day 112. Any subject whose baseline value for tetanus or VZV was above the detectable level at baseline, and is not within 30% of the baseline value or is below the detectable level by Day 112, will be referred to their primary care physician for further management. See Protocol Section 7.5.3 for additional information.
- h. PK: Starting on Days 0 and 28, serum samples will be collected just prior to the start of study drug infusion (pre-dose), and at 5 minutes and 2, 4, 6, 24, and 48 hours after the end-of-study drug infusion. Additional samples will be collected on Days 5 and 33. See Protocol Section 7.5.4 for additional information.
- i. Immunogenicity: Samples will be collected pre-dose when collected on dosing days. Samples will be collected on Days 0, 14, 28, 56, 84 and 112. See Protocol Section 7.5.6 for additional information.
- j. Prior to study drug infusion, SYNT001 drug product is to be diluted in dextrose 5% in water (D5W) to a total volume of 250 mL and administered intravenously over 1 hour using a 0.2-micron inline filter. See Protocol Section 4 and Section 7.8 for additional information.
- k. Immunoglobulins (IgG, IgA, IgM) and IgG subtypes (IgG1-4): Collected for measurements of IgG, IgG subtypes (IgG1-4), IgA, IgM at every visit. On Days 0, 7, 14, 21, and 28, samples are collected prior to infusion of study drug. See Protocol Section 7.5.5 for additional information.
- l. Exploratory pharmacodynamic samples (C3 and AECA): Collected pre-dose when collected on dosing days. See Protocol Section 7.5.5 for complete information.
- m. Buccal samples to be collected and stored; pending review of clinical and pharmacodynamics assessments.
- n. Immunophenotyping by flow cytometry for measurement of CD3+CD4+ T, CD3+CD8+ T, monocytes, NK cells and B cells.
- o. Photographs of active lesions taken prior to first dose on Day 0. Follow-up photographs will be taken at Days 33, 56, 84 and 112. Subjects who begin a steroid taper will have additional photographs taken at the clinic visit during which the decision to begin the taper is made.
- p. Visit Days 5, 12, and 19 may be conducted via at-home nurse in lieu of a subject visit to the study site.
- q. Subjects will return to the clinic on Days 84 and 112 for follow-up visits. Subjects whose total IgG is not within 30% of their Day 0 baseline value and not above 500 mg/dL at the Day 112 visit will be referred for further management.

Table 3. Study Assessment for Cohort 2

Visit Number	Screening	Loading			Maintenance					Follow-Up		
	1	2	3	4	5	6	7	8	9	10	11	12
Time Point (Study Day)	-14 to -1	0 Baseline	7 (±1 d)	14 (±1 d)	28 (±3 d)	42 (±3 d)	56 (±3 d)	70 (±3 d)	84 (±3 d)	91 (±5 d) or ET visit	112 (±5 d)	140 (±5 d) EOS
Informed consent	X											
Demographics/medical history	X											
Inclusion/exclusion	X											
Physical examination ^a	X	X	X	X	X	X	X	X	X	X		X
Vital signs ^b	X	X	X	X	X	X	X	X	X	X	X	X
Pulse oximetry ^c		X	X	X	X	X	X	X	X			
Clinical safety labs ^d	X	X	X	X	X	X	X	X	X	X	X	X
Pregnancy test ^e	X	X			X					X		X
Hepatitis and HIV screen	X											
12-lead ECG ^f	X	X		X	X					X		X
Tetanus and VZV antibodies ^g		X			X					X		X
PDAI ^h	X	X	X	X	X	X	X	X	X	X	X	X
PK sampling ⁱ		X	X	X	X				X			
Immunogenicity ^j	X	X	X	X	X	X	X	X	X	X	X	X
Study drug administration ^k		X	X	X	X	X	X	X	X			
Immunoglobulins (IgG, IgA, IgM) and IgG subtypes (IgG1-4) ^l	X	X	X	X	X	X	X	X	X	X	X	X ^q
CIC		X	X	X	X	X	X	X	X	X	X	X
Anti-Dsg (1 and 3) antibody titers	X	X	X	X	X	X	X	X	X	X	X	X
C3 and AECA ^m	X	X	X	X	X	X	X	X	X	X	X	X
FCGR2A by buccal swab ⁿ		X										
RNA sequencing		X			X					X		
Immunophenotyping ^o		X			X					X		
Exploratory pemphigus immune response biomarkers		X	X	X	X	X	X	X	X	X	X	X
Photography ^p		X	X	X	X	X	X	X	X	X	X	X

HR-QoL assessments		X			X					X		X
Adverse events	To be collected from the date that the ICF is signed through the last study visit											
Concomitant medications	To be collected from within 14 days prior to Day 0 through the last study visit											

Abbreviations: CIC = circulating immune complexes; d = day(s); ECG = electrocardiogram; EOS = end of study; ET= early termination; FcGR2a= Fc gamma R2a receptor; HIV = human immunodeficiency virus; HR-QoL = health-related quality of life; ICF = informed consent form; Ig = immunoglobulin; PDAI = Pemphigus Disease Area Index; PK = pharmacokinetic; VZV = varicella-zoster virus

- a. Complete physical examination, including weight, to be performed. Height and body mass index will be additional assessments conducted at screening only.
- b. Vital sign measurements (sitting blood pressure, heart rate, respiratory rate, and oral temperature) to be obtained after 5 minutes of seated rest. Any abnormal measurements are to be repeated after 5 minutes of rest. Vital sign measurements will be taken on all study visits. On dosing days, vital sign measurements will be collected immediately prior to the infusion; 15, 30, and 45 minutes after the start of the infusion; at completion of the infusion; and 30 minutes, 1 hour and 2 hours following completion of the infusion.
- c. Pulse oximetry: On dosing days, pulse oximetry to be measured immediately prior to the infusion; 15, 30, and 45 minutes after the start of the infusion; at completion of the infusion; and 30 minutes, 1 hour, and 2 hours following completion of the infusion.
- d. Clinical safety labs: hematology, clinical chemistry, and urinalysis. See Protocol Section 7.5 for a complete list. Full clinical safety lab draws will be collected at screening and at all study visits prior to infusion if applicable.
- e. Pregnancy test (women of childbearing potential only): To be performed at time of screening and prior to dose on dosing days if applicable. Urine or serum test is acceptable; however, positive urine tests must be confirmed with serum testing.
- f. Digital 12-lead ECG to be obtained after 5 minutes of rest in the supine position and in triplicate approximately 1 minute apart. See Protocol Section 7.6 for additional information. On days of treatment, to be obtained approximately 5 minutes after the completion of infusion.
- g. Serology: Any subject whose baseline value for tetanus or VZV was above the protective level at baseline and is not within 30% of the baseline value or is below the protective level by End of Follow-up, will be referred to their primary care physician for further management. See Protocol Section 7.5.3 for additional information.
- h. PDAI will be administered at screening. Subject eligibility requires a PDAI total activity score >4. Thereafter, assuming eligibility, the PDAI will be administered during Treatment Period and Follow-up Period. See Protocol Section 7.7 for additional information.
- i. PK: Starting on dosing days, serum samples will be collected just prior to the start of study drug infusion (pre-dose) and at 5 minutes, 1 and 2 hours after the end of study drug infusion. See Protocol Section 7.5.4 for additional information.
- j. Immunogenicity: Samples will be collected pre-dose when collected on dosing days. See Protocol Section 7.5.6 for additional information.
- k. Prior to study drug infusion, SYNT001 drug product is to be diluted in dextrose 5% in water to a total volume of 250 mL and administered intravenously over 1 hour ±15 minutes using a 0.2-micron, inline filter. See Protocol Section 4 for additional information.
- l. Immunoglobulins (IgG, IgA, IgM) and IgG subtypes (IgG 1-4): Collected for measurements of IgG, IgG subtypes (IgG1-4), IgA, and IgM at every visit. On dosing days, samples are collected prior to infusion of study drug. See Protocol Section 7.5.5 for additional information.
- m. Exploratory pharmacodynamic samples (C3 and AECA): Collected pre-dose when collected on dosing days. See Protocol Section 7.5.5 for complete information.
- n. Buccal samples to be collected pre-dose.
- o. Immunophenotyping by flow cytometry for measurement of CD3+CD4+ T, CD3+CD8+ T, monocytes, natural killer (NK) cells, and B cells. Collect samples pre-dose on dosing days.
- p. Photographs of all active lesions taken pre-dose on dosing days. Subjects who begin a steroid taper will have additional photographs taken at the clinic visit during which the decision to begin the taper is made.
- q. Subjects whose total IgG is not within 30% of their Day 0 baseline value and not above 500 mg/dL at the Day 140 visit will be referred for further management.

Table 4. Timing Window Allowances for PK/PD Sampling, ECG, and Vital Sign Measurements at Dosing Visits

Time Point	Tolerance Window	
	Cohort 1	Cohort 2
Pharmacokinetic Sampling		
0 hour	-240 minutes to 0 hour	-240 minutes to 0 hour
5 minutes post end-of-infusion	±5 minutes	±5 minutes
1 hour post end-of-infusion	N/A	±15 minutes
2 hour post end-of-infusion	±15 minutes	±15 minutes
4 and 6 hours post end-of-infusion	±15 minutes	N/A
24 hours (1 day) post end-of-infusion	±60 minutes	N/A
48 hours (2 days) post end-of-infusion	±120 minutes	N/A
Pharmacodynamic Sampling		
0 hour	-240 minutes to 0 hour	-240 minutes to 0 hour
24 hours (1 day) post end-of-infusion	±60 minutes	N/A
48 hours (2 days) post end-of-infusion	±120 minutes	N/A
ECG		
5 minutes post end-of-infusion	±10 minutes	±10 minutes
Vital Signs^a		
0 hour	-240 minutes to 0 hour	-240 minutes to 0 hour
15, 30, and 45 minutes after start of infusion	±5 minutes	±5 minutes
At completion of the infusion	±10 minutes	±10 minutes
30 minutes, 1 and 2 hours post end-of-infusion	±10 minutes	±10 minutes

Abbreviations: ECG = electrocardiogram; N/A = not applicable; PD = pharmacodynamics; PK = pharmacokinetic.

a. Vital signs to include blood pressure, pulse rate, respiratory rate, oral temperature, and pulse oximetry.

Table 5. Pharmacodynamic Assessments

Parameter	Collection Time Points	
	Cohort 1	Cohort 2 ^a
Immunoglobulins: 
 • IgG • IgG subtypes (IgG1-4) • IgA • IgM 	Screening and Days 0, 1, 2, 5, 7, 12, 14, 19, 21, 28, 29, 30, 33, 42, 56, 84, and 112	Screening and Days 0, 7, 14, 28, 42, 56, 70, 84, 91, 112, and 140

 • Circulating immune complexes (CIC) 	Days 0, 5, 7, 12, 14, 19, 21, 28, 33, 42, 56, 84, and 112	Days 0, 7, 14, 28, 42, 56, 70, 84, 91, 112, and 140

 • Albumin 	Screening and Days 0, 7, 14, 21, 28, 33, 42, 56, 84, and 112	Screening and Days 0, 7, 14, 28, 42, 56, 70, 84, 91, 112 and 140

 • Anti-Dsg (1 and 3) antibody titers 	Screening and Days 0, 7, 14, 33, 56, 84, and 112	Screening and Days 0, 7, 14, 28, 42, 56, 70, 84, 91, 112, and 140

 • C3 and AECA levels by indirect immunofluorescence 	Days 0, 14, 33, 56, 84, and 112	Screening and Days 0, 7, 14, 28, 42, 56, 70, 84, 91, 112, and 140

 • Exploratory biomarkers (RNAseq, urine IgG)^b 	Days 0, 14, 33, 56, 84, and 112	Days 0, 28, and 91

 • Immunophenotyping by flow cytometry for measurement of T cells, monocytes, NK cells, and B cells 	Days 0, 28, and 56	Days 0, 28, and 91

 • Exploratory biomarker (FCGR2A SNP, via buccal swab) 	Day 0	Day 0

 • Exploratory pemphigus immune response biomarkers 	Days 0, 5, 7, 12, 14, 19, 21, 28, 33, 42, 56, 84, and 112	Days 0, 7, 14, 28, 42, 56, 70, 84, 91, 112, and 140

^a Ongoing safety and PD evaluations may result in modification of the dosing regimen from every other week to weekly. See Protocol APPENDIX 5 for the corresponding visit schedule.

^b Urine IgG collected in Cohort 1 only.

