3.1.8 Serum Tetanus Antibody and Varicella-Zoster Virus Antibody Testing

Samples for serum tetanus antibody and VZV antibody testing are to be collected. Any subject whose baseline value for tetanus or VZV was above the protective level at baseline, and is not within 30% of the baseline value or is below the protective level by the end-of-study visit, will be referred to their primary care physician for further management.

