4.7.2 Clinical Laboratory Tests

Laboratory results, percentage change and absolute change from baseline will be summarized by cohort, visit and time point using descriptive statistics. Incidence of laboratory abnormalities and laboratory NCI CTCAE (Version 4.03) will be summarized. Shift tables of CTCAE Grade for chemistry parameters (Normal, Grade 1, Grade 2, Grade 3, Grade 4, Grade 3/4, Total, Missing) from baseline to each post-baseline time point showing number and percentage of subjects with movement between categories will be presented. The worst on-study grade after the first study drug administration will be summarized.

Baseline is defined as the Day 0 (pre-dose) measurement. If the baseline measurement is missing, the last measurement prior to the first study drug administration.

Results for variables that are not coded will be presented in the listings as below, within, and above the normal limits of the local laboratory.

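### The SAP states two incompatible tetanus/VZV referral rules for Cohort 1 (protective level versus detectable level), and the Cohort 1 titres at Days 84 and 112 exist only for subjects selected for a fall

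*SAP*

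**What the plan says.** Three places in the SAP set the rule for referring a subject whose tetanus or VZV antibody has fallen.

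- Section 3.1.8 covers any subject "whose baseline value for tetanus or VZV was above the protective level at baseline" who later "is not within 30% of the baseline value or is below the protective level by the end-of-study visit".
- Table 3, note g (Cohort 2) has the same baseline condition, and its level condition is that the subject "is below the protective level by End of Follow-up".
- Table 2, note g (Cohort 1) requires a baseline above the detectable level and refers a subject who "is not within 30% of the baseline value or is below the detectable level by Day 112".

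The Cohort 1 note also makes testing conditional. Day 56 is skipped if the baseline titre is undetectable. Day 84 is tested only "If the Day 56 results are greater than 30% below the baseline value, or if the subject falls below the level of detection". Day 112 is tested only if the Day 84 value is still below baseline or below detection. Note g to Table 3 has no such condition, and Table 3 schedules these titres after baseline on Days 28, 91 and 140.

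Section 3.1.5 lists serology as laboratory testing. Section 4.7.2 states: "Laboratory results, percentage change and absolute change from baseline will be summarized by cohort, visit and time point using descriptive statistics". It makes no exception for conditionally collected samples. Section 4 says missing data are not imputed unless otherwise stated.

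**The concern.** A protective level and a level of detection are different quantities. The SAP uses one in a rule that applies to everyone and the other in the rule for Cohort 1. Elsewhere in Section 3.1 the SAP spells out an intended cohort difference, for example for the PK parameters (3.1.9) and the spacing of ECG replicates (3.1.12). Section 3.1.8 does not, so the difference cannot be read as deliberate from the text.

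Safety is a primary objective, and the dose-selection endpoint seeks a total IgG fall of 60% to 90%. The tetanus and VZV titres are the antigen-specific check on what that fall does to existing vaccine and viral immunity. At stake are which Cohort 1 subjects count as having lost antibody, and whether the later Cohort 1 results describe the cohort or a subset chosen because it had fallen.

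**Working it through.** The SAP states no figure to reproduce. The check sets the rules side by side and then applies them to example titres.

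**Rules compared**

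| Provision | Applies to | Baseline condition | Level condition at end | Later titres |
|---|---|---|---|---|
| Section 3.1.8 | any subject | above protective | below protective | not stated |
| Table 2, note g | Cohort 1 | above detectable | below detectable | Day 56 if baseline detectable; Days 84 and 112 conditional |
| Table 3, note g | Cohort 2 | above protective | below protective | Days 28, 91 and 140 |

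All three share the 30% condition, so the disagreement lies in the level condition and in who enters.

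**Where the Cohort 1 rules diverge.** Set the protective level to 1 and assume a detection limit of 0.1. With baseline b and Day 56 value d, a subject crosses the protective level without triggering note g when b > 1, d < 1 and d ≥ 0.70b. This is possible only if 0.70b < 1, that is b < 1/0.70 = 1.43.

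| b → d | Fall | Section 3.1.8 | Table 2, note g |
|---|---|---|---|
| 1.30 → 0.95 | 0.35/1.30 = 26.9% | met | not flagged, not re-tested |
| 1.40 → 0.99 | 0.41/1.40 = 29.3% | met | not flagged, not re-tested |
| 1.30 → 0.85 | 0.45/1.30 = 34.6% | met | re-tested; met on this value |
| 0.80 → 0.50 | 0.30/0.80 = 37.5% | not covered (baseline not protective) | re-tested; met on this value |

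Rows 1 and 2 meet Section 3.1.8 only, and row 4 meets note g only, so neither rule contains the other. The first gap needs a detection limit below the protective level. If the limit lies between 0.70 and 1.00 of that level, fewer Day 56 values escape, because d must also be detectable.

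**Which titres exist.** A Cohort 1 subject with a detectable baseline who does not trigger at Day 56 has no titre at Day 84 or 112. A change after Day 56 in that subject is not measured. The 1.00 to 1.43 band does not count these subjects; the SAP gives nothing from which to count them.

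**Effect on a by-visit summary.** If Section 4.7.2 applies, the Day 84 statistics come only from subjects who fell by more than 30%, or to below detection, at Day 56. An invented example shows the direction. Eight subjects at Day 56, six at −10% and two at −40%, have mean (6 × −10 + 2 × −40)/8 = −17.5%. If the two recover to −32% and the other six are unchanged, the mean over all eight is (6 × −10 + 2 × −32)/8 = −15.5%, yet the table would show −32% (n = 2). The cohort has improved slightly and the table shows a decline.

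A simulation used only assumed inputs: log-normal Day 56 ratios with median change −10% to −30%, log-SD 0.15 to 0.25, half recovery by Day 84, and correlation 0.5 to 0.8. The mean Day 84 change was about −18% to −29% in re-tested subjects, against −2% to −14% had all been tested. The gap was about 5 to 27 percentage points, always toward a larger fall. The direction follows from the selection; the size follows from the assumptions.

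**The case against.** Several stronger readings are tempting, and the document does not support them.

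- **A loss of protection at Day 56 goes unseen.** It does not. Every Cohort 1 subject with a detectable baseline is due a Day 56 titre, and Section 4 lists all data. Such a loss is recorded but not flagged under note g. Only a loss after Day 56 in a subject not re-tested is unseen.
- **Section 3.1.8 cannot be applied in Cohort 1.** It sets its limit by, not at, the end-of-study visit, which can be read to include Day 56. The missing later value defeats only the narrower reading.
- **A biased table is certain.** Placing these titres under 4.7.2 is an inference from Section 3.1.5. That list also names PK, PD and ADA, which are analysed in 4.9. Section 4.7 speaks of clinical safety laboratory tests, which note d in both tables defines as hematology, clinical chemistry and urinalysis. This objection stands in part. If 4.7.2 does not apply, however, the SAP names no summary for these titres, and a sentence is needed either way. Section 4.1 requires n, so a reader would see the small count, though not that it arose by selection.
- **These titres are the only check on immunity.** Total IgG is also followed and has its own referral rule (note q in both tables).
- **Follow-up depends on which passage a site reads.** Both notes point to Protocol Section 7.5.3, which is not at hand, so nothing shows what sites act on.

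Comparability with Cohort 2 adds little, because safety analyses are descriptive and the regimens and test days already differ.

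**Conclusion.** The contradiction is explicit. For Cohort 1 the SAP gives two referral rules that differ in who enters and in what level counts as a loss. That neither contains the other rests on the assumption that the detection limit lies below the protective level. On that assumption, baselines between 1.00 and 1.43 times the protective level are exposed in one direction, and detectable but non-protective baselines in the other. How many of the up to 8 subjects fall there cannot be known from the SAP.

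The conditional testing is equally explicit. Subjects not re-tested have no value after Day 56, and any by-visit change statistic at Days 84 or 112 describes subjects selected for a fall. The shift is toward loss, and its size cannot be derived from the document. A reader might infer that one cut-off is the correct one; nothing here decides that, and it is a clinical matter.

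**What to change.** Reconcile Section 3.1.8, Table 2 note g and Table 3 note g, so that one consistent referral rule and timing is stated. The choice of cut-off and of testing schedule is the sponsor's.

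In Section 4.7.2, state how these titres are presented:

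- Do not present the conditional Cohort 1 Day 84 and Day 112 titres as by-visit means.
- Summarise Cohort 1 at Day 56, the last visit at which all subjects with a detectable baseline are tested. Give the number falling more than 30% and the number below the reconciled level.
- List the conditional re-tests, with the number eligible and the number tested at each day.

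A count based on each subject's worst post-dose titre would not serve as well, because it still depends on who was re-tested. The cost is wording in one section and two table notes, a sentence or two in 4.7.2, and one small table.
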